## **Introduction**

Vulvar Lichen sclerosus is a common benign dermatosis which causes pain and itching. Topical Steroids have been the main treatment modality. A recent study showed that fractionated CO2 laser treatment is non inferior and actually showed statistically significant improvement in subjective symptoms compared to clobetasol propionate steroid cream with no serious safety or adverse events. With steroids having a protective cancer benefit on lichen sclerosus, we hypothesize that steroids in addition to mona lisa laser will provide greater symptom relief while still providing the benefits of steroids on lichen sclerosus. This study will be following the clinical research protocol created and Good Clinical Practice standards and associated federal regulations.

## **Study Objectives**

To assess the efficacy of laser with use of topical steroid versus topical steroid treatment alone for lichen sclerosus symptoms

## **Study Design**

Primary Outcome: The primary outcome will be change in mean Skindex 29 score at 6 months.

Secondary Outcomes: Quality of life measurements using a subjective visual analog scale for bothersome vulvar symptoms, vulvovaginal symptoms questionnaire, and a global impression of improvement and satisfaction at six months. Secondary objective measures include provider assessment of vulvar appearance using an objective visual analog scale.

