## **Subject Selection and Withdrawal**

Inclusion Criteria: women with biopsy proven lichen sclerosus and significant symptoms based on Skindex-29 scores >21

Exclusion Criteria: prior vaginal mesh or pelvic radiation, or active genital infection

Subject Recruitment and Screening: The patients will be recruited by word of mouth in our OB/GYN clinic. Inclusion criteria includes biopsy proven lichen sclerosus.

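### Does defining the primary outcome as change in Skindex-29, in women selected for a high Skindex-29, let regression to the mean and lost precision into the primary comparison?

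*Protocol*

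**What the plan says.** Under Study Design the protocol states: "The primary outcome will be change in mean Skindex 29 score at 6 months". That sentence is the whole definition. It names no test, model or covariate, and neither requires nor excludes adjustment for baseline.

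Under Subject Selection and Withdrawal, women must have "significant symptoms based on Skindex-29 scores >21", so the entry criterion and the primary outcome use the same instrument. The protocol does not say whether the screening score also serves as baseline.

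The purpose is comparative in both places where it is given. Study Objectives reads "To assess the efficacy of laser with use of topical steroid versus topical steroid treatment alone for lichen sclerosus symptoms", and the Introduction says "we hypothesize that steroids in addition to mona lisa laser will provide greater symptom relief". The protocol gives no sample size, effect size, SD or analysis method, and does not describe how women are allocated to the two treatments.

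**The concern.** Three features together look troublesome.

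- **Selection on the outcome scale.** If the score that admits a woman is also her baseline, the group was chosen partly for upward measurement error. Its mean is then expected to fall on re-measurement even if nothing works.
- **Wording.** A change in a mean is naturally read as a before-after quantity in one group. Read that way, a fall in either arm could be mistaken for efficacy.
- **Efficiency.** A comparison of unadjusted changes is less precise than one adjusted for baseline, and it passes part of any chance baseline imbalance into the treatment difference.

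If the protocol really fixed a before-after or unadjusted analysis, the stakes would be a spurious improvement of several Skindex-29 points in each arm and a primary comparison weaker than the collected data allow.

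**Working it through.** The protocol gives no figure to reproduce. The only numerical input it supplies is the cut-off of 21. The rest are assumptions: clinic population mean μ of 25, 30 or 40, SD 15 or 20, correlation r between baseline and 6 months of 0.3, 0.5 or 0.7, normal scores, equal SD at both times, and the screening score used as baseline.

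**1. Size of the regression to the mean within an arm.** With a = (21 − μ)/SD and λ = φ(a)/(1 − Φ(a)), the expected fall without any treatment effect is (1 − r) × SD × λ.

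- μ 30, SD 20, r 0.5: a = −0.45, λ = 0.535, fall = 0.5 × 20 × 0.535 = 5.4 points.
- Smallest on the grid (μ 40, SD 15, r 0.7): 0.3 × 15 × 0.199 = 0.9 points.
- Largest (μ 25, SD 20, r 0.3): 0.7 × 20 × 0.675 = 9.5 points.

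The effect within an arm can therefore be sizeable.

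**2. What reaches the between-arm comparison.** The cut-off applies to every woman, so in comparable arms the expected fall is the same number in each. For the central case the difference is 5.4 − 5.4 = 0. A simulation with truncation at 21 and no treatment effect (μ 21, 30 and 40, SD 20, r 0.5 and 0.7) gave mean falls of 1.8 to 7.9 points, while the between-arm difference in change stayed within 0.05 points of zero.

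**3. Whether a change outcome rules out adjustment.** Write X for baseline, Y for the 6-month score and T for treatment. If Y = α + τT + βX + e, then Y − X = α + τT + (β − 1)X + e. Only the coefficient of X moves; τ and its standard error do not. In a simulated trial of 30 women per arm, both fits gave an estimate of −9.848 with standard error 2.995. Defining the outcome as change therefore costs no precision; only leaving out the covariate would.

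**4. Cost if the covariate were left out.** In units of SD², the adjusted residual variance is 1 − r². The variance of the unadjusted change among enrolled women is (1 − r²) + (1 − r)²k, where k is the variance of the baseline after the cut-off relative to before it.

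| μ, SD, r | k | Adjusted | Unadjusted change | Adjusted/unadjusted | SE inflation |
|---|---|---|---|---|---|
| 30, 20, 0.5 | 0.473 | 0.75 | 0.868 | 0.86 | 8% |
| 25, 20, 0.7 | 0.409 | 0.51 | 0.547 | 0.93 | 4% |
| 40, 15, 0.3 | 0.708 | 0.91 | 1.257 | 0.72 | 17% |

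The last two rows are the extremes of the grid.

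**5. Whether the cut-off aggravates this loss.** It does the opposite. Without selection k = 1 and the ratio is (1 + r)/2, which is 0.75 at r 0.5. With the cut-off it is 0.86 in the central case. Selection does lower the correlation among those enrolled, but it also shrinks the baseline variance that an unadjusted change carries, so the penalty (1 − r)²k becomes smaller.

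**The case for a change.** The best argument on the other side concerns wording, not efficiency. An outcome definition belongs in the protocol. Taken literally, this one is a before-after mean in a trial whose aim is a comparison, and the entry rule makes a before-after reading misleading. It is true that the sentence leaves the comparison implicit and that the baseline measurement is not identified. But the objective and the hypothesis are both plainly comparative, and nowhere does the protocol propose to infer efficacy from a fall within one arm. Read with those sections, the sentence names the quantity to be compared.

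A second argument is that allocation is not described, so comparable arms cannot be taken for granted, and an unadjusted change would pass a share (1 − r) of any baseline difference into the result, about half at r 0.5. The arithmetic is right. It still depends on an unadjusted analysis that the protocol does not specify, and baseline adjustment remains fully open. Uncertainty about allocation is a separate question from how the outcome is defined.

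**Conclusion.** The concern does not hold. The protocol fixes an outcome and a common entry threshold; it does not fix a raw, unadjusted or within-arm analysis. Regression to the mean of roughly 0.9 to 9.5 points per arm is plausible under the assumed inputs, but it has expectation zero in the between-arm contrast that the objective calls for, provided the arms are comparable, which the protocol gives no means of confirming. The precision loss, about 4% to 17% in standard error on the same assumptions, would arise only from an analysis stated nowhere in the document, and the entry cut-off reduces it. The choice of covariates is commonly left to a statistical analysis plan, and none is at hand. What remains is that the protocol could say which score is the baseline and that the change is compared between arms. No figure is wrong, and no passage contradicts another on this point.

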## **Subject Selection and Withdrawal**

Inclusion Criteria: women with biopsy proven lichen sclerosus and significant symptoms based on Skindex-29 scores >21

Exclusion Criteria: prior vaginal mesh or pelvic radiation, or active genital infection

Subject Recruitment and Screening: The patients will be recruited by word of mouth in our OB/GYN clinic. Inclusion criteria includes biopsy proven lichen sclerosus.

## **Early Withdrawal of Subjects**

Subjects that have any adverse effects, including worsening lichen sclerosus, severe irritation or any other safety reasons may withdraw from the study. Also subjects that do not adhere to the protocol may also be withdrawn. The subjects will also have to option to withdraw if they request.

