## **Study Procedures**

Risks: Risks to the subjects are minimal. The laser has been previously used for lichen sclerosus treatment and has been overall tolerated well. Potential side effects include vaginal irritation.

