## **Reporting Adverse Events**

Investigators are required to report all AEs experienced by subjects from the time of enrollment until the subject completes the study or terminates early. All AEs, regardless of their relatedness to the study device must be reported. The investigator will evaluate the intensity of the event, severity of the event, and its relatedness to the study device or procedure. All AEs must be followed until resolution or until they become stable.

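### The withdrawal rule lets non-adherent women be removed and does not separate stopping treatment from ending follow-up, so 6-month Skindex-29 scores may be lost selectively

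*Protocol*

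**What the plan says.** Early Withdrawal of Subjects gives three routes out.

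- Adverse effects: "Subjects that have any adverse effects, including worsening lichen sclerosus, severe irritation or any other safety reasons may withdraw from the study".
- Non-adherence: "Also subjects that do not adhere to the protocol may also be withdrawn". The sentence is passive, does not depend on a request, and does not define adherence.
- The woman's own request, listed separately.

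Study Design sets the primary outcome as "change in mean Skindex 29 score at 6 months". Study Objectives compares "laser with use of topical steroid versus topical steroid treatment alone". Study Procedures says of the laser: "Potential side effects include vaginal irritation".

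Reporting Adverse Events requires reporting "until the subject completes the study or terminates early", and adds: "All AEs must be followed until resolution or until they become stable". No section asks for a Skindex-29 from a woman who has stopped treatment or been withdrawn.

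**The concern.** The protocol treats leaving treatment and leaving the study as one event. Two of its grounds for leaving bear on the result. Worsening disease is close to what a symptom score measures, and adherence is part of how each strategy performs in practice. If women leave on these grounds and their 6-month score is not collected, those who remain are a selected group.

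The loss may also differ by arm. The combined arm has two treatments to adhere to and the control arm one, and irritation is the listed side effect of the laser. That would suggest more loss with laser, which would flatter the combination. Worsening on steroid alone could act the other way. A statistical analysis plan can choose an analysis set and a missing-data method, but it cannot recover scores that were never collected.

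**Working it through.** **Reading the text.** The non-adherence sentence stands apart from the request sentence, so it allows removal without a request. The adverse-effects sentence refers to leaving the study, not only the treatment. Early termination ends the reporting of new adverse events. Events already open are still followed, but no matching rule exists for the questionnaire.

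**Inputs.** From the protocol: the 6-month Skindex-29 change, the entry cut of more than 21, and the two arms. The protocol shows no SD, correlation, sample size or dropout rate, so there is no figure to reproduce and everything below is assumed. Higher scores are worse. A negative difference (combination minus steroid alone) favours the combination. There is no true difference between arms, and only observed scores are compared.

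**1. Removal for non-adherence.** Let q be the share removed in an arm, and d the number of points by which removed women do worse than retained women. Then

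retained mean = mean of all women − q × d,

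spurious difference = −(q_combination − q_steroid) × d.

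- 10% v 20% (steroid alone v combination): −0.10 × 5 = −0.5; −0.10 × 10 = −1.0.
- 10% v 30%: −0.20 × 5 = −1.0; −0.20 × 10 = −2.0.

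**2. Loss of women who worsen.** Baseline and 6-month scores are bivariate normal with mean 30, SD 20 and correlation 0.5, keeping baselines above 21 (8,000,000 draws). Mean change is −5.35, which is regression to the mean only. If a share p of women worsen, with mean change w, and a fraction L of them is lost, then

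observed mean change = (−5.35 − p × L × w) / (1 − p × L).

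Take any rise as worsening: p = 0.39 and w = 12.96 in the simulation. L = 0.25 gives (−5.35 − 0.0975 × 12.96) / 0.9025 = −7.33. L = 0.50 gives (−5.35 − 0.195 × 12.96) / 0.805 = −9.79. The difference is about −2.46 with these rounded inputs and −2.45 unrounded. All cases (simulation error about 0.01), loss shown as steroid alone v combination:

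| Worsening: rise of more than | Share of women | 25% v 50% lost | 10% v 50% lost | 25% v 50% lost, both arms improving 10 points more |
|---|---|---|---|---|
| 0 points | 39.0% | −2.45 | −3.69 | −1.55 |
| 10 points | 20.6% | −1.55 | −2.40 | −0.77 |
| 20 points | 8.6% | −0.77 | −1.22 | −0.30 |

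The shares apply to the base case. For 25% v 50%, the share of all women lost is 0.25 and 0.50 times that column: 9.75% v 19.5%, 5.15% v 10.3%, and 2.15% v 4.3%. Equal loss (25% in both arms, or 50% in both) gives 0. Swapping the rates between arms reverses the sign.

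**Sensitivity.** Changing one input at a time (mean 40, SD 15 or correlation 0.7), 25% v 50% gives −1.90 to −2.69, −1.01 to −1.82 and −0.35 to −0.98 for the three definitions.

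**3. Effect on the test.** In SD units, the bias is the difference in withdrawal rates times the gap g between retained and withdrawn women. With g from 0.25 to 1.0 SD and withdrawal of 10% v 5% up to 30% v 10% (laser v steroid), the bias runs from 0.05 × 0.25 = 0.013 SD to 0.20 × 1.0 = 0.20 SD. With an assumed 64 women per arm, the chance of a false positive in that direction rises from 2.5% to between 2.9% and 17%.

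**The case against.** Only the non-adherence sentence lets the study remove a woman who has not asked to leave. The adverse-effects sentence reads most naturally as her own choice, so the fix recovers those scores only where she still agrees to follow-up. This stands: the recoverable part of that loss is unknown.

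The larger figures belong to loss of worseners, not to the non-adherence rule. For that rule the range is 0.5 to 2.0 points, or about 0.03 to 0.11 of the simulated SD of change (0.5/18.6 and 2.0/18.6). The simulation also triggers loss on the final score, whereas withdrawal would follow interim status. That would generally give a smaller bias. A milder imbalance, 10% v 20% of worseners lost, gives 0.80, 0.56 and 0.30 points. These points stand, and the bias may be small.

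Unequal loss is an inference. The protocol calls the risks minimal, describes the laser as generally well tolerated, and calls the expected irritation mild. The withdrawal wording is permissive, and the adverse-event reporting window says nothing directly about questionnaires. If non-adherence means missed questionnaires, deleting the ground recovers little.

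None of this removes the main point. Used as written, the rule can end follow-up for reasons tied to the outcome, and nothing in the protocol provides for the 6-month score afterwards.

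**Conclusion.** The concern holds, as an improvement that should be made rather than a flaw that defeats the trial. The text establishes that non-adherent women may be removed unasked, that worsening disease is a named ground for leaving the study, and that the primary outcome is not protected after either. Selective loss is therefore possible to the extent the rule is used. Unequal loss between arms is plausible but not shown, and its direction cannot be known from the protocol. On assumed inputs, the false difference runs from 0 with equal loss to 2.0 points for non-adherence, and to about 3.7 points in the most unequal base-case loss of worseners. Confidence is medium, because every input to these sizes is assumed.

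**What to change.** In Early Withdrawal of Subjects:

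1. Delete withdrawal from the study for non-adherence, and record adherence instead.
2. State that stopping study treatment, for any reason, does not end study participation.
3. State that Skindex-29 and the secondary questionnaires are collected at 6 months from every woman who has not withdrawn consent to follow-up.

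Decisions on stopping treatment and each woman's right to withdraw are unchanged. The cost is a wording change plus one 6-month questionnaire contact for each woman who stops treatment. Some of that contact is already required: under Adverse Event and Reporting Adverse Events, worsening of a pre-existing condition during the study is an adverse event to be followed until it resolves or is stable.

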## **Study Procedures**

Risks: Risks to the subjects are minimal. The laser has been previously used for lichen sclerosus treatment and has been overall tolerated well. Potential side effects include vaginal irritation.

## **Adverse Event**

An AE is defined as any untoward medical occurrence, regardless of its relationship to the study device or the study procedure. An untoward medical occurrence includes any new, undesirable medical experience

or worsening of pre-existing condition, which occurs at any point from the start of treatment to the final visit.

### **Expected Morbidity/Anticipated Adverse Events**

An expected morbidity/procedural complication is defined as an AE that is known to be common or usual in nature, severity, or incidence during treatment. Post laser vaginal mild irritation is expected and will not be documented as an adverse event unless the investigator considers the pain or fever to exceed that normally anticipated during laser treatment.

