### **Severity of Adverse Effect**

It is the investigator's responsibility to assess the severity of an AE. A change in severity may constitute a new reportable AE.

The following guideline should be used to determine the severity of each adverse event:

- Mild: awareness of experience, but easily tolerated. No medical intervention required.
- Moderate: enough discomfort to interfere with usual activities. Medical Intervention required.
- Severe: inability to carry out usual activities. Medical intervention (including hospitalization or prolongation of hospitalization) required

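### Mild post-laser irritation is exempted from adverse event recording, against the protocol's own all-events rule and in the laser arm only

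*Protocol*

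**What the plan says.** Five sections of the Protocol bear on whether mild irritation after laser is recorded.

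- **Adverse Event** gives the definition: "An AE is defined as any untoward medical occurrence, regardless of its relationship to the study device or the study procedure". It covers new experiences and worsening of existing conditions, and makes no exception for expected events.
- **Expected Morbidity/Anticipated Adverse Events** first places expected events inside that definition: "An expected morbidity/procedural complication is defined as an AE that is known to be common or usual". It then takes one of them out: "Post laser vaginal mild irritation is expected and will not be documented as an adverse event". The only limit on this exemption is an override left to judgement, worded as follows: "unless the investigator considers the pain or fever to exceed that normally anticipated during laser treatment".
- **Severity of Adverse Effect** provides a lowest grade: "Mild: awareness of experience, but easily tolerated. No medical intervention required".
- **Reporting Adverse Events** sets the duty: "Investigators are required to report all AEs experienced by subjects". It states no exception and does not refer to the expected-morbidity section.
- **Study Procedures**, under risks, names one side effect of the laser: "Potential side effects include vaginal irritation".

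The comparison, from **Study Objectives**, is "laser with use of topical steroid versus topical steroid treatment alone".

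**The concern.** There are two problems. First, the same event is an AE that must be reported under one section and an AE that is not to be documented under another, and nothing says which section governs. Investigators may settle this differently from patient to patient.

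Second, the exemption is tied to the laser. Only patients given laser can have post-laser irritation, so the same symptom at the same grade is recorded by different rules in the two arms. The exempted event is also the only laser side effect that the Protocol names. An AE table or tolerability statement by arm would therefore make the laser arm look better tolerated than it was. This is a rule about data collection, so an analysis plan cannot repair it: what was not recorded cannot be tabulated.

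**Working it through.** The Protocol states no irritation rate, sample size or safety threshold, so it has no figure to reproduce. The check is mainly a comparison of sections.

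**Step 1: is the event an AE?** Yes. Mild irritation after laser is an untoward occurrence under the general definition, which disregards relationship to device or procedure. The expected-morbidity section itself calls such events AEs.

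**Step 2: is a mild AE meant to be recorded?** Yes. The severity scale has a grade for easily tolerated events that need no intervention, and the reporting section covers all AEs.

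**Step 3: what does the exemption do?** It removes this one mild AE from documentation. Taken literally, steps 1 and 2 require the record and step 3 forbids it.

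**Step 4: in which arm does it act?** The control is topical steroid alone and no sham laser is described, so it acts in the laser plus steroid arm only. Mild irritation under steroid alone stays under the general rule and is recorded if judged new or a worsening.

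**Step 5: when does the exemption lift?** The exempted event is irritation, but the override refers to pain or fever. It gives no test for irritation itself. This is an ambiguity about the trigger; it does not exempt fever.

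**Step 6: possible size.** All rates here are assumptions. Let p_L be the true rate of mild post-laser irritation and e the share of those cases left out.

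- Recorded laser-arm rate = p_L × (1 − e)
- Under-recording = e × p_L

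| Case | p_L | e | Under-recording (percentage points) |
|---|---|---|---|
| Low | 10% | 25% | 0.25 × 10 = 2.5 |
| Middle | 20% | 50% | 0.50 × 20 = 10 |
| High | 40% | 100% | 1.00 × 40 = 40 |

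If investigators follow the exemption to the letter, e is close to 100% and nearly the whole of p_L is lost. Lower values of e stand for sites that partly follow the all-AEs rule instead.

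**Step 7: effect on the gap between arms.** Let p_S be the true rate under steroid alone and u the share of those cases not recorded, for example because they are put down to the underlying disease.

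- Bias in the recorded gap = −(e × p_L) + (u × p_S)

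Take true rates of 40% against 20% (gap +20 points) and e = 25%:

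- u = 0: recorded 30% against 20%, gap +10, bias −10.
- u = 25%: recorded 30% against 15%, gap +15, bias −10 + 5 = −5.

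The laser-arm rate is too low by 10 points in both cases. Only the gap depends on what happens under steroid alone.

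**The case against.** The strongest reply is that the exemption is a specific exception to a general rule. It has its own heading, names one event and carries an override. The reporting section qualifies its duty by relatedness to the device, which concerns causality and not expectedness, and the mild grade still serves every other mild event. On that reading an investigator can act on the text, and a cross-reference would close the drafting gap. Leaving out an expected, mild procedural effect is then a design choice.

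This reading is available and softens the contradiction. It does not touch the asymmetry: a deliberate exception tied to the laser still applies in one arm only.

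Other points carry some weight:

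- **Small consequence.** The Protocol lists no safety endpoint and no between-arm AE test, it discloses irritation as a risk, and it names severe irritation as a ground for withdrawal. This limits the importance of the point but does not remove it.
- **Assumed rates.** They are all assumed and the range is wide. That is correct; the numbers illustrate scale and the conclusion does not rest on them.
- **Other data sources.** Patients complete a visual analog scale for vulvar symptoms and a vulvovaginal symptoms questionnaire. The stated time point is six months, so they would not reliably pick up short-lived irritation after a laser session.
- **Sham laser.** One-sidedness assumes that none is used. The wording of the control supports this, but it remains an assumption.
- **Pain as a measure of irritation.** Pain can be read that way, which leaves fever as the stray term in the override. The wording point is minor.

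**Conclusion.** The concern holds. As written, the Protocol classes mild post-laser irritation as an AE, requires all AEs to be reported, and then says this one will not be documented. Whether that is read as a contradiction or as a deliberate exception, the laser plus steroid arm is under-recorded for the only laser side effect the Protocol names.

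The direction of the error in the laser-arm rate follows from the text. Its size cannot be determined from the Protocol. The direction of the error in the gap between arms also depends on how fully mild irritation is recorded under steroid alone. The one-sidedness rests on there being no sham laser in the control arm.

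The damage is to descriptive safety and tolerability reporting, so this should be fixed but does not threaten the efficacy result.

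**What to change.** Reconcile the sections on the AE definition, expected morbidity and AE reporting as follows:

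1. Delete the non-documentation rule.
2. State that irritation of any grade is recorded as an AE by the same rule in both arms, using the existing severity grades.
3. Keep the notion of expectedness as a flag: mark mild post-laser irritation as *anticipated* in the AE listing instead of omitting it. Tables can then show AEs with and without anticipated events.
4. Replace the override with a statement that pain and fever are recorded under the general AE rule.

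A cross-reference in the reporting section would remove the textual conflict but leave the one-arm asymmetry, so it is not enough alone.

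The change concerns recording only. It costs protocol wording, a few more AE form lines per laser patient, and a higher count of mild AEs in the laser plus steroid arm.
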